3.3.2 AEs - general

AEs experienced by any subject at any time during the entire study will be coded using the latest version of the Medical Dictionary for Regulatory Activities (MedDRA).

AEs will be summarised for analysis according to their onset date into the following study periods:

- AEs occurring during screening/run-in period: date of Visit 1 \leq AE onset date < date of first dose of IP

- AEs occurring during on-treatment period: date of first dose of IP \leq AE onset date \leq minimum (date of last dose of IP + 35 days, date of death, date of study withdrawal)
- AEs occurring during post-treatment period (for subjects still being followed up then): date of last dose of IP + 35 days $<$ AE onset date \leq study completion or withdrawal date
- AEs occurring during on-study period: date of first dose of IP \leq AE onset date \leq study completion or withdrawal date.

If the AE has a completely missing (and unresolvable) onset date, then the AE will be assumed to have occurred during the on-treatment period, unless the end date indicates unambiguously that the AE resolved before treatment started. If the AE has a partially missing (and unresolvable) onset date, then the AE will also be assumed to have occurred during the on-treatment period, unless either the end date indicates unambiguously that the AE resolved before treatment started, or the partial onset date is in the month/year prior to start of treatment.

Exposure adjusted incidence rates will be defined as the number of subjects reporting adverse events divided by extent of exposure for each subject, where exposure will be defined (irrespective of whether they have had the AE) as in 3.3.1 for extent of exposure for the on-treatment summaries.

Study adjusted incidence rates will be defined as the number of subjects reporting adverse events divided by duration of the on-study period for each subject as defined in Section 3.1.5.

The total time at risk (years) for a treatment group will be derived as the sum of the individual subject times at risk (days) for that treatment group and divided by 365.25.

For exposure-adjusted summaries of all AEs, the time at risk for each subject will be calculated using the first formula based on date of last dose of IP for all subjects, irrespective of whether they have had the AE.

In all exposure-adjusted summaries of AEs, multiple occurrences of the same event for a particular subject will not be counted as separate events. A subject will either be considered to have no events of the type being summarised, or one or more occurrences of that event.

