- If two non-missing values are recorded on the same day and have no assessment time associated with at least one of them, or the same assessment time associated with both of them, the average of the two values will be selected for analysis at that visit.
- If there are multiple ADA samples in the same visit window with both positive and negative results, the sample with a positive result and the highest titre value should be selected.

If a subject has no value within a particular visit window, then the subject will have a missing value at that visit in summaries and analyses.

The same visit window definitions below will be used regardless of whether the planned treatment, on-treatment, or on-study period is used for analysis (see Section 3.1.5). In practice, each data record in the planned treatment period will be identified, and then additional flags are created according to whether it is in the on-treatment or post-treatment, or on-study periods. These flags will be used to select all eligible records for subsequent visit windowing, according to whether the derived visits are to be used in a planned treatment, on-treatment, or on-study period analysis. It should be noted that, if treatment was discontinued within a particular visit

window, the rules above for handling multiple values within the same visit window could select a different record according to whether a planned treatment period analysis or an on-treatment period analysis is needed.

In planned treatment period analysis, any off-treatment assessments measured at a follow-up visit (scheduled 16 weeks after last IP administration) which occurred earlier than scheduled follow-up visits week 32, week 36, week 40, or later due to COVID-19 pandemic will be considered in earlier planned treatment period visit windows, where applicable.

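### An adverse event whose partial onset date lies wholly after the on-treatment period is still counted as on-treatment, because the rule makes exceptions only for dates before treatment

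*SAP*

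**What the plan says.** SAP Section 3.3.2 classifies AEs by onset date. The on-treatment period runs from first dose to "minimum (date of last dose of IP + 35 days, date of death, date of study withdrawal"). The post-treatment period, for subjects still in follow-up, is "date of last dose of IP + 35 days $<$ AE onset date \leq study completion or withdrawal date".

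A separate paragraph of the section deals with incomplete dates. Where part of the onset date is missing and cannot be recovered, the rule reads "then the AE will also be assumed to have occurred during the on-treatment period, unless either the end date indicates unambiguously". This first exception concerns events that were over before dosing began. The second exception is worded "or the partial onset date is in the month/year prior to start of treatment".

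Other sections that bear on the point:

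- Section 3.1.6 describes the follow-up visit as "any off-treatment assessments measured at a follow-up visit (scheduled 16 weeks after last IP administration"). Section 1.2 gives a 12-week follow-up and encourages subjects who stop investigational product (IP) early to stay for the full 40 weeks.
- Section 3.1.7 covers medications with a partial start date. It presumes an on-treatment start when the known month or year coincides with that of the end of IP treatment.
- Section 4.2.8.1 summarises AEs for the on-treatment and on-study periods. Post-treatment AEs are listed but not summarised separately.
- Sections 3.3.1 and 3.3.2 set the denominator of the exposure-adjusted rates to exposure time, capped at last dose + 35 days.

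**The concern.** A default to on-treatment is sensible when the known part of a date leaves the period in doubt. The SAP accepts that the known part can remove that doubt, since it exempts a month or year before treatment. It does not apply the same logic at the other end. An onset recorded only as September, in a subject whose on-treatment period ended on 10 July, cannot be on-treatment on any day of that month, yet the rule assigns it there.

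Two kinds of output are exposed. On-treatment counts of AEs, SAEs and AESIs can include events known to have started later. In the exposure-adjusted summaries the numerator gains such events while the denominator excludes the time in which they arose, so absolute on-treatment incidence is pushed upward.

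**Working it through.** The SAP gives no figure for this point, so there is none to reproduce. The check has three parts.

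**1. The rule applied to one case.** Take a last dose on 10 June 2019.

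- End of on-treatment: 10 June + 35 days = 15 July 2019.
- Final follow-up: 10 June + 112 days = 30 September 2019.
- AE onset recorded as August 2019, day unknown and not recoverable.
- By the period definitions, every day of August is after 15 July and before 30 September, so the event is post-treatment.
- By the partial-date rule, August is not before treatment. If the end date does not show resolution before treatment either, neither exception applies and the event is on-treatment.

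The same section therefore gives two answers for one event.

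**2. Whether the case can arise.** Inputs are the on-treatment limit of 35 days (Section 3.3.2) and final follow-up at 16 weeks (Section 3.1.6).

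- Length of the post-treatment window: 16 × 7 - 35 = 112 - 35 = 77 days, that is days 36 to 112 after the last dose.
- I enumerated every last-dose date in 2019 and 2020 (731 dates) with every onset day from 36 to 112 (731 × 77 = 56,287 combinations).
- The window contains two full calendar months for 410 of the 731 dates and one for the other 321, so there is always at least one.
- The onset month is later than the month in which on-treatment ends in 80.9% of combinations. For individual last-dose dates the share runs from 61% to 100%.
- If only the year is known, the onset year is later than the year in which on-treatment ends in 10.7% of combinations.
- For a subject who stops after the first dose and is followed to week 40, the window is 40 × 7 - 35 = 245 days.

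**3. What one subject is worth.** Section 1.3 plans 55 subjects per arm. One subject is 1/55 = 1.8% and two are 2/55 = 3.6%. The common-AE table in Section 4.2.8.1 uses a threshold of more than 3% in either group, so one reassigned subject can decide whether a preferred term appears in the on-treatment version of that table.

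**The case against.** The strongest defence is that the partial-date paragraph is an explicit convention for incomplete data, that it errs toward counting events as on-treatment, and that this is the cautious direction for safety. The effect is also limited:

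- On-study summaries and study-adjusted rates run from first dose to study completion, so they do not change and no event is lost.
- Exposure-adjusted summaries are planned for all AEs only, so the mismatch does not reach separate SAE or AESI rate tables.
- Counts are of subjects. A misplaced event alters a preferred-term row only if the subject had no on-treatment occurrence of that term.
- The rule is the same in both arms of a double-blind trial, and no mechanism for differential bias has been shown.
- The 81% is conditional on a post-treatment onset with month and year known. It does not measure how many events are affected.

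All five limits stand, and they keep this a modest point. The appeal to caution does not justify the rule where nothing is uncertain: if the known month settles the period, counting the event as on-treatment is misclassification. Nor can the word *unresolvable* be read as meaning that the period cannot be determined, because the existing exception for a month or year before treatment would then have no purpose.

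**Conclusion.** The concern holds. Section 3.3.2 assigns to the on-treatment period events that its own definitions place after it, and no other section of the SAP supplies the missing exception. Among AEs starting on days 36 to 112 after the last dose and dated only by month and year, about 81% would be misassigned; among those dated by year alone, about 11%. Both figures assume that last-dose dates and onsets are spread evenly and that follow-up reaches day 112.

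The absolute number cannot be derived, because the SAP gives no frequency of partial onset dates; it is probably small. The consequence is an upward bias in absolute on-treatment counts and exposure-adjusted rates. No efficacy result and no on-study summary is affected. The rule should be corrected, but it does not threaten the trial's main conclusions.

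**What to change.** Add a third exception to the partial-date rule in Section 3.3.2. If the known part of the onset date (month and year, or year alone) is later than the corresponding part of the date on which the on-treatment period ends, the AE is assigned to the post-treatment period. Keep the on-treatment default wherever the partial date is compatible with the on-treatment period, including an onset month equal to the month in which that period ends.

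The cost is one clause in the SAP and one condition in the AE date program, preferably settled before unblinding. On-treatment counts may fall slightly. The events concerned stay in the on-study summaries and appear in the listing of post-treatment AEs.

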3.3.3 Adverse events of special interest

The protocol specifies AESIs as those which merit special attention in this trial, and for which derivation details (for those derived from the eCRF), or a statement when the derivation needs to be referenced externally to the SAP (for those derived from MedDRA dictionary terms), are given in Appendix 8.1.

Similar considerations apply to any additional supporting analysis of AESIs, in which MedDRA dictionary based definitions are used.

3.3.4 Laboratory variables

Clinical chemistry, haematology and urinalysis will be performed by a central laboratory according to the schedule and the variable specifications described in the CSP. Urine samples will be analysed locally and sent for analysis at the central laboratory only if a positive dipstick result for any parameter is observed.

Changes from baseline in continuous laboratory variables will be calculated at relevant visits as specified in Section 3.1.1 and Section 3.1.2.

In all analysis of continuous laboratory variables, any value recorded only as below lower limit of quantification (LLOQ) will be set to LLOQ and included in the analysis. Any value recorded only as above upper limit of quantification (ULOQ) will be set to ULOQ and included in the analysis. Absolute values will be compared to the relevant normal reference range, as provided by the central laboratory, and classified as low (below range), normal (within range or on the limits) or high (above range). All values falling outside the normal reference ranges will be flagged. These classifications will also be used for shift tables.

For the purposes of shift tables, baseline will be defined as specified in Section 3.1.1. Minimum, maximum and last values calculated across all visits in the relevant study period will use all available values including those from unscheduled and repeat visits, and irrespective of whether the values have been selected for use in summaries using visit windows (see Section 3.1.6).

Liver function tests for aspartate aminotransferase (AST), alanine aminotransferase (ALT), alkaline phosphatase, and total bilirubin (TBL) will also be evaluated as multiples of the upper limit of the normal reference range (ULN). Subjects who meet any of the following criteria at any time during the study will be flagged:

- $AST \geq 3 \times ULN$
- $ALT \geq 3 \times ULN$
- $TBL \geq 2 \times ULN$

Other multiples of ULN will also be used in the display of liver function tests.

3.3.5 Vital signs

Changes from baseline in vital signs variables (pulse rate, systolic blood pressure (BP), diastolic BP, respiratory rate, body temperature, body weight, and BMI) will be calculated at relevant visits as specified in Section 3.1.1 and Section 3.1.2.

BMI is calculated as:

$$BMI = Weight (kg) / [Height (m)]^2.$$

Absolute values and changes from baseline (where applicable) will be compared to the relevant reference range tabulated below, and classified as low (below range), normal (within range or on the limits) or high (above range). All values falling outside the reference ranges will be flagged.

Table 2 Vital signs reference ranges

Parameter	Standard units	Lower limit	Upper limit	Change from baseline criteria
Diastolic blood pressure (sitting)	mmHg	60	100	±15

Table 2 Vital signs reference ranges

Parameter	Standard units	Lower limit	Upper limit	Change from baseline criteria
Systolic blood pressure (sitting)	mmHg	90	160	±30
Pulse rate (sitting)	Beats/min	50	100	±20
Respiratory rate	Breaths/min	8	20	
Body temperature	Celsius	36.0	37.5	
Weight	kg	40	150	

3.3.6 Electrocardiogram

Either 12-lead or 15-lead ECG measurements will be recorded in accordance with the protocol, with the baseline visit being defined as V1.

The outcome of the overall evaluation (normal, abnormal or borderline) will be taken directly from the eCRF, as will the assignment of clinically significance.

3.3.7 Physical examination

Complete and brief physical examinations will be performed at time points according to the SoA in the CSP. Assessments will be dependent on whether the examination is complete or brief, as described in Section 8.2.3 of the CSP. For the brief physical examination, only information on whether the assessment was performed or not is to be recorded.

Only physical examination results judged as a new clinically meaningful finding or a clinically meaningful aggravation of an existing finding by the investigator will be captured, and these will be reported as AEs.

3.4 Derivation of pharmacokinetic and immunogenicity variables

Serum samples for determination of tezepelumab concentrations and the presence of anti-drug antibodies (ADAs) will be collected at baseline prior to first IP administration, at multiple time points and before any IP administration during the treatment period, and at the end of the follow-up period, according to the SoA in the CSP. BAL samples will also be collected for determination of tezepelumab concentration at specified time points according to the SoA in the CSP.

Serum samples will be used to determine tezepelumab concentrations, and to measure the presence of ADA, according to validated assays performed by a designated third-party vendor. Tezepelumab concentrations in BAL will be evaluated using a qualified assay and reported separately from the CSR. Urea concentrations in both serum and BAL will also be evaluated using qualified assays to correct for the dilution factor of the BAL samples. Details of the bioanalytical methods used will be described in a separate bioanalytical report.

For immunogenicity, tiered analysis will be performed to include screening, confirmatory, and titre of ADA assay components. Samples that are confirmed positive for ADAs will be archived for possible testing for the presence of neutralizing antibodies (nAb).

The third party vendor analysing the PK samples will be unblinded to the randomised treatment assignments of all subjects; no one from the study team will have access to the PK or ADA data until after the study has been unblinded. The assay for determination of tezepelumab concentrations in serum or BAL will only be performed using samples for subjects randomised to tezepelumab. Subjects who are randomised to placebo will not have their PK samples analysed by the vendor laboratory. The ADA and urea samples from all subjects, regardless of treatment assignment, will be analysed.

Due to the limited sampling schedule, only tezepelumab concentration data will be available (for the tezepelumab group only); no other PK parameters will be derived for any analysis within the scope of this SAP.

4. ANALYSIS METHODS

4.1 General Principles

4.1.1 Statistical hypotheses for efficacy variables

The primary efficacy objective will be evaluated through statistical testing of the within subject change, expressed as a ratio, from baseline to EOT in number of airway submucosal inflammatory cells separately for eosinophils, neutrophils, T cells (CD3+, and CD4+), mast cells tryptase+, and mast cells chymase+. Subjects will be analysed using the evaluable analysis set with subjects classified by their randomised treatment according to the ITT principle.

The null hypothesis test H_0 will be: The ratio (tezepelumab/placebo) of the change, expressed as a ratio, from baseline to EOT for each primary and secondary endpoint between tezepelumab and placebo equals 1 and will be tested versus. H_1 : The ratio (tezepelumab/placebo) of the change, expressed as a ratio, from baseline to EOT for each primary and secondary endpoint between tezepelumab and placebo is not equal to 1, i.e.,

H_0 : ratio (tezepelumab/placebo) = 1

H_1 : ratio (tezepelumab/placebo) \neq 1

4.1.2 Testing strategy to account for multiplicity considerations

The statistical testing of change from baseline to EOT for each of the primary variables will be performed separately for eosinophils, neutrophils, T cells (CD3+, and CD4+), mast cells tryptase+, and mast cells chymase+.

The testing of individual secondary efficacy variables will be considered as supportive.

Nominal p-values will be reported for primary and secondary variables i.e. no adjustment of multiplicity will be performed.

The descriptive statistics will be summarised for primary, secondary and exploratory efficacy endpoints, safety, pharmacokinetic and immunogenicity variables.

4.2 Analysis methods

4.2.1 Subject disposition, demography and baseline characteristics

Subject disposition will be summarised using the all subjects analysis set. The number of enrolled subjects will be summarised. The number and percentage of subjects within each treatment group will be presented by the following categories: randomised, not randomised (and reason), received IP, did not receive IP (and reason), completed treatment, discontinued treatment (and reason), discontinued treatment but completed study assessments, completed treatment and completed study, completed study (subjects who completed IP and study, and subjects who discontinued IP but completed study assessments), and withdrawn from study (including reason). Subject recruitment by country and centre will also be summarised.

Disposition will also be provided for the number and percentage of randomised subjects who consented separately to participate in the optional sub-studies (e.g. DNA sampling).

The number and percentage of subjects, who discontinued IP, but remained in the study will be presented by treatment group and option of follow up (Section 1.2).

Kaplan-Meier plots will be produced summarising separately the time (in days) to last dose of IP and premature withdrawal from the study by randomised treatment group using FAS. Subjects without the premature event will be censored as described in Section 3.1.9.

Demographic data such as age, gender, race, and ethnic group (Hispanic or Latino, Not Hispanic or Latino) will be summarised by randomized treatment group using FAS. The stratification factor i.e. blood eosinophils count (< 150 cells/ μL , $150 - < 300$ cells/ μL , ≥ 300 cells/ μL) recorded at screening will be summarised by randomised treatment using FAS. All subgroups as defined in Section 3.1.8 will be summarised by randomised treatment group using FAS.

Various baseline characteristics will also be summarised by randomized treatment using FAS. These include respiratory disease histories, weight, height, BMI, smoking status, history of allergy, FEV1 (pre- and post-BD) and FEV1 reversibility, FEV1 % predicted (pre and post-BD), FVC (pre and post-BD), FEF_{25-75%} (pre and post-BD), FEV1/FVC(pre and post-BD), asthma duration, age at onset of asthma, asthma medications, the number of asthma exacerbations in the previous 12 months, number of asthma exacerbations requiring hospitalisations in the previous 12 months, and ACQ-6. The medical and surgical histories will be summarised by randomized treatment using FAS.

Baseline biomarker variables FeNO, blood eosinophils, allergic status, total serum IgE, baseline cytokines IL-5, and IL-13 will also be summarised by randomized treatment using FAS.

Medical and surgical histories will be summarised by MedDRA Preferred Term (PT) within the System Organ Class (SOC) level of MedDRA using FAS.

The demographic, subject characteristics at baseline, lung function at baseline, asthma characteristics at study entry, relevant disease related treatment at baseline will also be summarised by randomised treatment group using evaluable analysis set.

Important PDs will be summarised by randomised treatment using FAS.

The number and percentage of subjects in each of the analysis sets defined in Section 2.1 will be summarised.

4.2.2 Prior and concomitant medications

The number and percentage of subjects receiving each medication (by ATC classification system codes and generic name) will be presented by randomised treatment using FAS. Separate tables will be presented for all medications received during each of the following periods as defined in Section 3.1.7: prior, concomitant (on-treatment), concomitant (post-treatment).

Tables for maintenance medications (started on or prior to and ongoing after the first day of IP) will be produced. The number of subjects using ICS medications and other maintenance asthma medications at visit 1 and baseline, and baseline total daily dose of ICS medications will be summarised using FAS. The number of subjects using ICS medications and other maintenance asthma medications at baseline will also be summarised using evaluable analysis set. In addition, the total number of days of systemic corticosteroid treatment associated with asthma exacerbations per subject from the first day of IP to EOT will also be summarised.

Summary statistics will be produced of total daily OCS dose converted to a prednisone equivalent (for subjects taking OCS at baseline). Conversion factors to be applied for this purpose are given in [Appendix 8.2](#).

Disallowed medications will include medications defined as prohibited according to Section 6.5 of the CSP. Disallowed medications include prohibited and restricted drugs; restricted drugs are considered a disallowed medication depending on timing of use, or if there are changes in dose and regimen during the study as defined in the CSP. They will be defined following a physician review (prior to database lock) of the unique combinations of ATC code classifications and generic terms captured.

Separate tables will be presented for all allowed and disallowed medications received during each of the following periods as defined in Section 3.1.7: prior, concomitant (on-treatment), concomitant (post-treatment), respectively.

Medications will be classified using the latest version of the WHO Drug Dictionary.

Percentages will be calculated relative to the number of subjects in FAS.

Data from subjects who discontinued IP, regardless of level of follow up chosen will, where possible and relevant, be included in the appropriate medication summaries.

Potential prior biologics use will be summarised separately, similarly to above.

